## Innovation

The proposed project is **innovative** in a number of ways: 1) we use a project design that emerged organically from expertise in the community, 2) we integrate two successful and culturally appropriate approaches in a novel way, 3) we use a multi-level socioecological approach to address social and structural determinants, and 4) we incorporate future advocacy to address structural barriers.

Community-based Innovation: At the same time that Latina MEH is an enormous concern in NM, there are two contextual factors at play that offer opportunities for us to develop a novel way to address women’s concerns while promoting health equity. The proposed project will **leverage existing resources and knowledge in an innovative, culturally-appropriate way**. This strengths-based approach integrates wisdom and evidence from community work and research in NM related to CHWs and Latina social dynamics. We will implement a **group navigation model that combines CHW-assisted navigation with peer group support**. This approach was conceptualized by Principal Community Mentor and Co-Investigator, [name], a CHW with over 20 years’ experience. [name] recognizes the synergistic nature of factors that negatively influence MEH outcomes for Spanish-speaking Latinas, including social Isolation, depression, and other emotional disorders. In her CHW role, [name] has encountered Latinas with significant MEH that are not currently being addressed through the existing health care system. The novelty of this pilot is in recognizing and addressing these conditions as interrelated in order to develop strategies to counter disparities in treatment and access.

Building on the Existing CHW Model: In NM, a robust effort has been made to develop a systematic approach to helping people navigate health systems and access community resources through the creation of a variety of important CHW programs. These programs have been shown to successfully

address health needs of New Mexicans who would otherwise lack information about or access to resources and services. Currently, most NM CHW programs tend to involve interaction between a CHW and an individual client. The relationship between the CHW and the client can be very personal and in best-case scenarios, is culturally-appropriate. However, we believe that this interaction could be further strengthened by incorporating a group dynamic with the capacity to contextualize MEH within the context of peer validation and support for the recognition of the effect of everyday stressors. **Our innovative model builds on existing CHW approaches, allowing women to receive both individual and group support to address their needs, while developing personal relationships and increasing understanding of social determinants that influence their lives.**

Recognizing the Importance of the Social-Relational: Research among Latinos has demonstrated the centrality of social relationships and peer support as factors influencing Latina MEH. **The proposed intervention will innovatively integrate CHW navigation with peer support using a novel structured dialogue approach that combines expert group facilitation with open-ended discussion to allow participants to share experiences and insights, and to define themes discussed with support from the facilitator.** Structured dialogue can be empowering for women through the development of positive personal strategies for dealing with MEH. Examples of empowerment include strengthening interpersonal relationships, learning about and navigating systems to access resources, improving “literacy” of social and structural dynamics that influence individual, family and community health, and feeling socially connected.

Eliciting Explanatory Models (EM): Kleinman developed the elicitation of EM to understand how social worlds affect and are affected by illness. EM are now widely used in medical schools and clinical settings. Doctors ask, “What do you call this problem?” and “What do you believe is the cause of this problem?” in an effort to open dialogue with patients to reveal their understanding of illness and treatments. **As a methodological innovation of the proposed project, a facilitator of the same cultural background as participants ([name]) who is also trained in Western conceptualizations of MEH, will elicit EM from participants in a group setting.** Using structured dialogue, this process will allow participants to develop personal and collective MEH conceptual repertoires. As such, [name] will bi-directionally translate understandings of MEH and facilitate identification of appropriate treatments.

### **Approach**

Theoretical Model: The model in the study is informed by **socioecological approaches** to address disparities and affect change at **multiple levels** as broadly constructed by a **social and structural determinants of health framework.** We included attention to change at the level of the individual, the social group, and external infrastructure (e.g. political, legal, economic and other social/institutional factors). Our pilot addressed social and structural determinants at each of these levels.

Research Design: We use a **convergent parallel mixed method research design** to implement an intervention to affect **six domains of interest** in the lives of Latinas: 1) emotional support, 2) informational support, 3) depression, 4) social isolation, 5) empowerment, and 6) social determinants needs. Further, we will assess the feasibility of implementing this model with 30 participants. The intervention integrated navigation assistance and case management by a CHW with a peer support group. We gathered both qualitative and quantitative data using a variety of instruments and methods as described below, and we will integrate different types of data during analysis and interpretation.

Team Expertise & Roles: Our transdisciplinary team integrated expertise from anthropology, community-engaged research, social work, counseling, community navigation, and biostatistics, and we are well situated to conduct the proposed research. **[name] [name], the PI**, is a cultural anthropologist and Research Assistant Professor of Pediatrics in the Prevention Research Center. She has over 20 years’ experience conducting community-engaged research with migrants and other marginalized people to improve health and well-being. **[name], Principal Community Mentor and Co-Investigator**, was trained as a Special Education teacher in Aguascalientes, Mexico and

**Population:** This project involved Spanish-speaking Latinas from low-income households. Participants was recruited from the International District and South Valley neighborhoods of Albuquerque and screened for language, self-reported ethnic identity as Latino/Hispanic, and self-reported income below 250% of the Federal Poverty Level. The majority of the participants were Mexican immigrants with one participant who was from Central America and one who was a second generation Mexican immigrant.

**Recruitment:** During month #2 prior to the start of the intervention, [name] recruited 30 participants through the Pathways Program, the Simplemente Salud Clinic and Centro Sávila. In the course of regular meetings with clients who request a range of services, she identified identify and invite those who might benefit from the proposed model. While participants experessed interest int eh program, lower numbers than anticipated joined the study from the first 3 cohort. We therefore changed the implementation strategy to allow for two sequential cohorts, one in the Fall and and one in the Spring.

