**Aim 1. Create a group navigation model to improve mental and emotional health equity for Spanish-speaking Latina women.** In a series of peer group sessions facilitated by [name], a CHW who designed the model, we will create a culturally-appropriate, non-stigmatizing group intervention. The group process will allow participants to explore their own MEH, better understand the ways that mental health influences well-being and everyday dynamics of their lives, and to develop empowering knowledge and action plans through the support of other women. We will document group discussions, processes, and themes, gather information about women's explanatory models of MEH, and administer a multidimensional survey to capture information about the domains of interest. Through individual case management, [name] will work individually with women from the groups to identify their specific social and structural determinants needs, assist them to make an individual action plan, provide them with information about available resources, and help them navigate systems and access resources and services. We will document participant needs and navigation outcomes. **Hypotheses:** Participation will decrease depression, social isolation, and social determinants needs, and increase emotional support, informational support, and women's sense of empowerment.

**Aim 2. Create an advocacy plan.** With data gathered in group meetings and individual navigation sessions, we will identify social and structural barriers that negatively influence participants' MEH outcomes and ability to access resources and services. We will create an advocacy plan to address structural and policy barriers that can be implemented by CHWs and advocacy groups in the future. **Hypotheses:** We can identify factors that negatively influence the MEH and well-being of Latinas. We hypothesize that in the future, we can use this knowledge to develop a strategic plan with the potential to address socio-structural and policy barriers through advocacy.

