## Significance

Latina MEH Disparities: New Mexico (NM) is one of five majority-minority states with 48% of the population identifying as Hispanic, a group that experiences poor health outcomes. Moreover, there is evidence of an “immigrant paradox” or “nativity effect,” wherein recent immigrants experience mental and emotional health (MEH) disorders at lower rates than native born Hispanics. However, others have cautioned that Hispanics/Latinos are not a monolithic group even within the immigrant community.

More recent research has shown that social-structural conditions negatively influence the health of the immigrant population, with significant disparities in the realm of MEH. In particular, providers in Albuquerque’s International District have identified MEH as a significant concern among Spanish-speaking Hispanic women (Latinas), especially those from the Mexican immigrant community.

Through our research and community work with this population, members of our team have found that Latinas often: 1) misrecognize MEH symptoms and are unsure how they can be addressed through existing community resources, 2) require assistance identifying and navigating systems and services, 3) lack social and emotional support, and 4) experience personal disempowerment.

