| NMPHA (Present Advocacy Plan)                    |       |   |   |   |   |   |   |   |   |    | ■  |    |
| Report results in Community Venues               |       |   |   |   |   |   |   |   |   |    |    | ■  |
| Final Report for TREE Center                     |       |   |   |   |   |   |   |   |   |    |    | ■  |

addressing stigma, recognizing the prevalence depression and anxiety, investing in self and life purpose, developing coping skills, self-esteem, agency/empowerment and emotional awareness. 2) Family: recognizing/helping other family members, redefining family in U.S. context; 3) Community: Providers-knowing who to see, what questions to ask; Organizational—what organizations offer, which are accessible. Finally, these results can inform administrative/systems/policy change to improve mental health equity for Spanish-speaking Latina women.

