### **Conclusions**

The study showed that interventions designed by community members effectively address barriers to addressing MEH (sociocultural attitudes and responses to MEH, current context and effects on Latinas). The research broadened our understanding of how MEH is impacted by sociocultural, economic, and policy-level factors is necessary to create effective interventions for addressing MEH. Preliminary results offer insight into how multilevel change is needed to improve mental health equity.

The recruitment process showed that potential participants recognized a great need for such interventions among Spanish-speaking Latinas, but stigma, as well as family and work obligations made it difficult for women to commit to the class at the outset. However, the benefits of attending the class have spread by word of mouth, if funding were to be found for continued intervention, it is certain that there would be robust participation. Another major limitation for this project and community-based work generally were the bureaucratic barriers/mismatch between the university and the community-based organizations to ensure timely payment for the organization. Additionally, survey completion during class was a barrier. In the future, a plan to collect baseline and follow-up data in person would make the first session flow better and be less intimidating for participants.

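### Conclusions makes a claim about community-designed interventions as a class, but the study observed one uncontrolled intervention, led by its designer, in mostly Mexican immigrant women from one city

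*Combined protocol and SAP*

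**What the plan says.** **Conclusion drawn.** Conclusions opens with: "The study showed that interventions designed by community members effectively address barriers to addressing MEH". The subject is plural, the verb reports something shown, and nothing restricts it to this study.

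**Who took part.** Approach, Population, describes low-income, Spanish-speaking Latinas "recruited from the International District and South Valley neighborhoods of Albuquerque". It adds: "The majority of the participants were Mexican immigrants with one participant who was from Central America and one who was a second generation" Mexican immigrant.

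**Who led it.** Specific Aims, Aim 1, has the group sessions facilitated by "a CHW who designed the model, we will create a culturally-appropriate, non-stigmatizing group intervention", and the same aim assigns the individual case management. Innovation, under Eliciting Explanatory Models, presents as a methodological innovation the use of "a facilitator of the same cultural background as participants".

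**What the authors say about heterogeneity.** Significance notes that "others have cautioned that Hispanics/Latinos are not a monolithic group", extends the caution to the immigrant community itself, and mentions a nativity effect on mental health.

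**Limitations listed.** Conclusions names stigma and family or work obligations as obstacles to joining, payment bureaucracy between university and community organizations, and the difficulty of completing surveys in class.

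**The concern.** A conclusion about a class of interventions needs more than one member of that class, or an argument that the one observed stands for the rest. Here there is one intervention. Its designer led it, so the effect of the model cannot be separated from the effect of the person. Cultural match between facilitator and participants is part of the method, so the findings are conditional on that match. With no comparison group, the pre/post changes cannot be attributed to the intervention with confidence.

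Aim 3 hypothesises that the model is feasible, acceptable, valuable and culturally appropriate, and Specific Aims makes the pilot the foundation for an R21 application. A reader who takes the class-wide sentence at face value would believe that effectiveness across community-designed interventions has been shown. The limitations give that reader no warning about origin mix, the single lead CHW or the single city.

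**Working it through.** The question is what the design can support, so there is no figure in the plan to reproduce. Its only design calculation, a detectable effect of d = 0.53 with 30 participants, concerns pre/post change scores and does not bear on transfer to other interventions or populations.

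**Step 1: what the claim needs against what was observed.**

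| Element of the claim | Observed | Where |
|---|---|---|
| Interventions designed by community members (plural) | One | Specific Aims, Aim 1; Approach, Intervention Implementation |
| Shown to be effective | No comparison group described; baseline and follow-up only | Approach, Research Design and Quantitative data collection |
| Independent of who delivers it | One lead CHW, who is also the designer | Specific Aims, Aim 1 |
| Independent of setting | Two neighborhoods of one city | Approach, Population |
| Independent of participants' origin | Mostly Mexican immigrants; one Central American and one second-generation participant named | Approach, Population |

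With one intervention there is no between-intervention variation to estimate. With one named woman in each other group, no separate assessment by origin or nativity is possible, whatever the total enrolment.

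**Step 2: do the reported results carry the claim anyway?** Results reports an increase in resiliency as the strongest quantitative finding. Social, emotional and informational scores improved without statistical significance, and depression scores worsened, which the authors suggest may reflect the psychoeducation component. The intervention is reported as acceptable and feasible. These findings fit a preliminary statement about this intervention. They do not supply the missing generality.

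**Step 3: is the claim qualified elsewhere?** Conclusions calls its results preliminary, but in a separate sentence about the need for multilevel change. That sentence does not limit the opening claim. None of the listed limitations touches the rows in the table.

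**The case against.** The strongest reply is that the sample suits the stated need and is openly described. Significance says providers see the problem especially in the Mexican immigrant community, and Approach discloses the origin mix and the neighborhoods. Both points stand. They justify the choice of sample, but they do not justify an unrestricted sentence about other interventions.

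Several stronger readings are tempting, and the documents do not support them:

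- **Overreach to all Latinas.** A reader might take "to improve mental health equity for Spanish-speaking Latina women" in Results as a claim that the findings hold for all such women. It is the end of a hedged clause saying that the results can inform administrative and policy change. It names whom that change should serve, which is the target population of Aim 1.
- **A percentage.** A reader might infer that all but two women were Mexican immigrants, for example 28/30 = 93%. The text says the majority and gives no count. Enrolment is also unclear: 30 recruited is followed by a report of lower numbers than expected.
- **Cultural fit in other groups not assessed.** Both women of other background took part, and nothing excludes them from the evaluation. The accurate statement is that there were too few to assess separately.
- **Sole delivery by one CHW.** Names are removed, and a second person assisted in the classes. A single lead is supported; sole delivery is not.
- **A mis-targeted R21.** The documents do not state the target population of that application.

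**Conclusion.** The point holds for the opening sentence of Conclusions and for the gap in the limitations. The sentence generalises from one intervention, one lead CHW who was also its designer, one city and no comparison group, in a mostly Mexican immigrant sample with one named participant in each of two other groups. No percentage is needed, and none can be given reliably.

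This rests on two readings. The first is that the lead facilitator and the designer are the same CHW, as Aim 1 states. The second is that no comparison group existed, since none is described. The facilitator is described as sharing participants' cultural background; the documents do not say that she matched each woman's origin.

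The correction changes what may be concluded from the pilot. It does not undermine the pilot's design or its feasibility findings.

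**What to change.** 1. Replace the opening sentence of Conclusions with one about this intervention only, for example: *In this uncontrolled pilot, one group navigation intervention, led by the CHW who designed it, gave preliminary indications of helping mainly Mexican immigrant, low-income women in two Albuquerque neighborhoods with barriers to addressing MEH.*
2. Add to the limitations, for example: *Most participants were Mexican immigrants from one city, and the model was led by a single CHW, its designer, who shared their cultural background. There were too few other Latinas to assess cultural appropriateness separately, and the model cannot be separated from the person who led it.* Refer back to the caution on heterogeneity in Significance.
3. Leave the hedged sentence on policy change in Results as it is; it states the target population.
4. Do not report the accounts of the two women of other background separately. In a sample this small, from named neighborhoods and recruitment sources and with themes that include domestic violence, that could identify them.

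The cost is a few sentences of wording and a narrower conclusion. No new data or analysis are required.

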#### Intervention Implementation:

**MONTH #1:** Planning, logistics, & preparation.

**MONTH #2:** Recruitment.

**MONTH #3:** During month #3, each cohort of 10 participants participated in four two-hour classes held weekly and facilitated by [name] with assistance from [name]. Class 1 included introductions and open-ended discussion of participants' perspectives on and experiences with MEH challenges including eliciting explanatory models of illness using a structured dialogue approach. In Class 2, [name] presented information on concepts of MEH including anxiety, depression, and social isolation, and the group explored ways that participants' own experience may align with these concepts. In Class 3 participants identified and give name to their feelings and experiences and begin to consider services they might be interested in accessing. In Class 4, [name] provided information about relevant health care and other resources, for example, school counselors, domestic violence services, Centro Sávila, The Hopkins Center, couples counseling, UNM mental health services/counseling, and church support groups.

**MONTH #4:** Over the first three weeks of month #4 of the intervention, the team conducted a preliminary analysis of class notes, observations and audio (described in the data analysis section below) to identify common themes and specific resource and service needs for each participant, and in week 4 of month #4, reconvene the groups for Class 5 to discuss findings and individual experiences with accessing resources and services since Class 4 and individual participants will develop action plans.

**MONTHS #5-7:** [name] provided individual case management to assist participants to access resources and navigate systems to achieve goals identified in their individual action plans.

**MONTH #8:** We reconvened the groups for Class 6 to engage in a follow-up discussion of outcomes and to administer the post-survey.

Mixed method data collection.

| Construct                | Instrument              | # of Items | Time point |
|--------------------------|-------------------------|------------|------------|
| Demographic Info         |                         | 18 items   | B only     |
| Depression               | PHQ-9                   | 9 items    | B&F        |
| Emotional Support        | PROMIS  | 8 items    | B&F        |
| Informational Support    | PROMIS     | 8 items    | B&F        |
| Social Isolation         | PROMIS     | 8 items    | B&F        |
| Resiliency               | CD-RISC                 | 25 items   | B&F        |
| Adverse Childhood Events | ACES                    | 10 items   | F          |
| ACES Resiliency          | ACES + Resiliency       | 12 items   | B&F        |
| Eval & Feasibility       |                         | 8 items    | F          |

*Quantitative data collection:* Data was stored in a database created in UNM's secure data capture system, REDCap. We tracked recruitment, attrition, attendance at group sessions, and attendance at individual CHW navigation meetings. Pre-/Post-data was gathered at baseline (Class 1) and follow-up (Class 6) in the form of a multi-dimensional survey (see table). The survey will include: A) demographic questions to characterize participants, B) program evaluation/feasibility questions to document participant experiences with and perceptions of the group process, working with the CHW, and the value of the intervention, C) seven reliable instruments that have been validated in English and Spanish to measure the six domains of interest: a) emotional support, b) informational support, c) social isolation ; d) depression; e) ACES; and f) resiliency.

*Qualitative data collection:* Group class sessions were audio-recorded. [name] and/or [name] attended Classes 1 and 6 for each cohort and take observational notes. Analytical notes taken during team meetings. Notes from individual case management sessions, individual resource action plans, and the Advocacy Plan will be documented and analyzed.

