and deductive approach, coupled with the recognition that study participants and researchers 'co-construct' data, thus making it a good fit for community-engaged research. As such, analyses require inclusion of participant perspectives and meaning to be fully developed. A key aspect of this approach is its iterative nature, thus analysis will be ongoing and begin at baseline. Beginning in Month 3, notes from audio recordings were checked for accuracy and imported into NVivo 11, a qualitative data analysis software program. [name] trained [name] in qualitative coding techniques and all qualitative data will be independently coded by [name] and [name]. Analysis began with 1) text-based coding, marking recurrent themes or statements, 2) as themes emerge, [name] and [name] met to define and standardize them, agree on a structural framework and to determine how themes should be applied to coding, 3) [name] and [name] used focused coding of prominent thematic clusters and constant comparison techniques to conduct preliminary analysis of prominent themes, 4) we conducted member checking through sharing these preliminary interpretations during Class 4, using methods developed by CBPR researchers to elicit feedback and interpretation from the group, which we then incorporated into our analyses. For Aim 1, qualitative analysis of narratives from class discussion and observational notes provided insights into women's explanatory models of MEH to inform the case management and resource access phase of the intervention, the dynamics of the structured dialogue group process, how women develop and use action plans to navigate and access resources, how they explain and describe their experience in this process, and the extent to which empowering processes emerge. For Aim 2, we analyzed challenges and barriers identified by participants and identify potential strategies to promote institutional and policy changes that would positively affect MEH through advocacy. Aim 3 was assessed by looking at evaluation process data for participant perspectives on the feasibility, acceptability, value and cultural appropriateness of the intervention model.

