## Results

Intervention was acceptable and feasible. Increase in resiliency was our most robust quantitative finding. Social, emotional and informational empowerment scores improved, but not in statistically significant way. Depression scores worsened, which could reflect the effectiveness of the psychoeducation component. Qualitative results: participants' experiences in the intervention underscored the importance of recognizing cultural differences in values and meaning related to MEH: 1) Self-advocacy and self-efficacy (learning how to say "no" or set limits as Latinas) ; 2) Addressing violence (in domestic settings, in families, social violence) ; 3) Isolation and socializing (recognizing differences in U.S. v. Latin America) . Overall, the results demonstrated the importance of multilevel interventions that address mental health at multiple levels: 1) Individual:

| Research Timeline                                | Month |   |   |   |   |   |   |   |   |    |    |    |
|--|-------|---|---|---|---|---|---|---|---|----|----|----|
|  | 1     | 2 | 3 | 4 | 5 | 6 | 7 | 8 | 9 | 10 | 11 | 12 |
| Activity   |       |   |   |   |   |   |   |   |   |    |    |    |
| Planning/Logistics                               | ■     |   |   |   |   |   |   |   |   |    |    |    |
| Recruitment                                      |       | ■ |   |   |   |   |   |   |   |    |    |    |
| Cohort 1 (Classes 1-4)                           |       |   | ■ |   |   |   |   |   |   |    |    |    |
| Quantitative Baseline Interview                  |       |   |   |   |   |   |   |   |   |    |    |    |
| Cohort 2 (Classes 1-4)                           |       |   |   | ■ |   |   |   |   |   |    |    |    |
| Cohort 3 (Classes 1-4)                           |       |   |   |   | ■ |   |   |   |   |    |    |    |
| Analysis of Class Data                           |       |   |   |   | ■ | ■ |   |   |   |    |    |    |
| Class 5 – Discuss Findings, Resource Access Plan |       |   |   |   |   | ■ | ■ |   |   |    |    |    |
| Individual Case Management                       |       |   |   |   |   |   | ■ | ■ | ■ |    |    |    |
| Class 6 – Follow-up to Discuss Outcomes          |       |   |   |   |   |   |   |   | ■ |    |    |    |
| Quantitative post-interview                      |       |   |   |   |   |   |   |   |   | ■  |    |    |
| Data Analysis of Outcome Class                   |       |   |   |   |   |   |   |   |   | ■  | ■  |    |

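### The acceptability and value ratings for Aim 3 come only from women reached at Class 6, and no route is specified to ask those who stopped or missed it

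*Combined protocol and SAP*

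**What the plan says.** The instrument table in Intervention Implementation lists the evaluation items as "Eval & Feasibility | | 8 items | F", so they are given at follow-up and at no other time. The quantitative data collection paragraph below it fixes what follow-up means: "Pre-/Post-data was gathered at baseline (Class 1) and follow-up (Class 6) in the form of a multi-dimensional survey (see table". Under Month #8 the same section states: "We reconvened the groups for Class 6 to engage in a follow-up discussion of outcomes and to administer the post-survey". By then a woman has been offered four weekly classes, Class 5 and three months of individual case management.

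The items ask how women found the group sessions and the CHW's help, and what the program was worth to them. No other structured instrument in the plan covers these topics.

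Aim 3 (Specific Aims) also promises to track recruitment, drop-out, and attendance at classes and navigation meetings, and to collect qualitative data. Class sessions are audio-recorded and case-management notes are kept. The qualitative part of Data Analysis says "Aim 3 was assessed by looking at evaluation process data for participant perspectives", without defining evaluation process data. The Results report a favourable conclusion on both acceptability and feasibility. They give no attrition figure, no number of respondents and no criterion.

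**The concern.** Aim 3 hypothesises acceptability, value and cultural appropriateness as well as feasibility. A woman who leaves after Class 2, or who comes to every class but misses Class 6, supplies no rating on the only structured measure of the first two. If women who leave think less well of the program than women who stay, ratings from Class 6 overstate acceptability. The attendance log will show that a woman left, but not why or what she thought.

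This matters beyond the pilot. The Specific Aims present the study as the foundation for an R21 application, and reasons for stopping are what a designer of the next study would want to know.

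**Working it through.** **Is there a plan figure to reproduce?** Not for Aim 3: the documents state no target share, threshold, attrition rate or count of respondents. The only design figure is the detectable effect of d = 0.53 with 30 participants for the Aim 1 change scores. A two-sided paired t-test at 0.05 gives power 0.801 for those inputs, so the figure reproduces. This point does not touch it.

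**Timing.** Class 1 is in month 3 ("During month #3, each cohort of 10 participants participated in four two-hour classes held weekly") and Class 6 in month 8, so the items come 8 − 3 = 5 months after the start. The Research Timeline under Results differs. It has three cohorts starting in months 3, 4 and 5, Class 6 in month 9, and a separate row, "Quantitative post-interview", in month 10. On the chart, Class 6 falls 9 − 5 = 4 to 9 − 3 = 6 months after a cohort's start, and the post-interview 10 − 5 = 5 to 10 − 3 = 7 months after. The Recruitment paragraph adds that delivery was changed to two sequential cohorts, which the chart does not show.

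**Size of the possible bias.** Let N women start, m answer at Class 6, and k of those be favourable.

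- Observed share: k/m.
- Share among all starters: at least k/N (no unasked woman favourable) and at most (k + N − m)/N (all of them favourable).
- Width of the interval: (N − m)/N, which is the fraction not asked.
- Bias of the observed share: (fraction not asked) × (share among those asked − share among those not asked).

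All the counts below are assumptions, with N = 30:

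| Answer at Class 6 (m) | Favourable (k) | Observed | Lowest, all starters | Highest, all starters |
|---|---|---|---|---|
| 25 | 23 | 23/25 = 92% | 23/30 = 77% | 28/30 = 93% |
| 21 | 19 | 19/21 = 90% | 19/30 = 63% | 28/30 = 93% |
| 20 | 18 | 18/20 = 90% | 18/30 = 60% | 28/30 = 93% |

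The bias formula agrees with the last row. With one third unasked, the bias is 1/3 × (0.90 − 0) = 0.30 at one extreme and 1/3 × (0.90 − 1) = −0.03 at the other. If every respondent is favourable, the observed figure is 100% whatever the attrition. The floor is then 27/30 = 90% at 10% attrition, 24/30 = 80% at 20%, 21/30 = 70% at 30%, 18/30 = 60% at 40% and 15/30 = 50% at 50%.

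When the observed share is high, the interval reaches much further below it than above. The bias is zero if women who leave hold the same views as those who stay.

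**The case against.** The strongest reply is that Aim 3 does not rest on these items alone. Recruitment, attrition and both kinds of attendance are tracked, and they count women who leave. Class audio records a woman for as long as she attends, and someone who misses only Class 6 may have contributed to five earlier classes and to case-management notes. A reader might infer that all of Aim 3 is judged by women who stayed. The documents do not support that, and on feasibility this objection stands. It does not close the gap on acceptability and value. Counts carry no opinions, and the recordings are of discussions led by the CHW who designed the model, where no one is systematically asked to evaluate it.

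A reader might also infer that leavers were never asked. That is a conclusion from silence: the separate post-interview row in the timeline leaves another contact possible, although it describes no outreach to leavers. The supportable statement is that no route is specified.

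Nor can the Conclusions be used to say who dropped out. The sentence "stigma, as well as family and work obligations made it difficult for women to commit to the class at the outset" concerns recruitment. That the same pressures affect retention is plausible but not documented.

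Finally, the plan defines no percent-favourable endpoint, and the Recruitment paragraph says fewer women joined than expected, so 30 starters is itself uncertain. Asking for a verdict on the whole intervention at its end is also a defensible choice for a small pilot. Both points are fair. They limit the claim about size and argue for keeping the Class 6 items, but they do not justify leaving women who stop without a question.

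**Conclusion.** The point holds for the structured acceptability and value ratings. As written, they are conditional on being reached at Class 6, and they are probably biased upward. The direction rests on the assumption that women who leave are, on average, less favourable. Some will miss Class 6 for reasons unrelated to the program, so the direction is likely but not certain. The size cannot be estimated without an attrition figure, and the percentages above only show how wide the uncertainty becomes. Attendance at Class 6 may not have secured an answer either, because the Conclusions name survey completion in class as a barrier.

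The feasibility conclusion is not undermined in the same way. This is an inexpensive improvement worth making and a reason to qualify the acceptability conclusion. It is not evidence that the intervention was unacceptable.

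**What to change.** 1. Have an existing team member other than the CHW phone every woman who attended Class 1 but stopped or missed Class 6. Put to her the evaluation items that apply to the parts she received, plus one question on her reason for leaving.
2. Report the number answering and the ratings out of all Class 1 attendees. Show leavers separately, and give best-case and worst-case bounds for those not reached.
3. Qualify the acceptability conclusion in the Results accordingly. If calls are no longer possible, steps 2 and 3 can still be done from the attendance log, and exit contact can be built into the R21 design.
4. Asking the group-process items at about Class 4 as well is optional. Given the reported barrier to completing surveys in class, keep them very short or collect them outside class. Navigation has not begun by then, so those ratings cover only part of the intervention.
5. Reconcile the text (post-survey at Class 6, month 8) with the timeline (Class 6 in month 9, post-interview in month 10), and state which applied to the cohorts actually run.

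The cost is a few phone calls and a possibly less favourable acceptability figure.
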